#### **10.2.2.5 Fat-soluble Vitamin Deficiency (FSV)**

Patients with cholestatic liver disease are at risk for the development of FSV

deficiency. The investigator should assess patients for the following signs and symptoms of FSV deficiency at screening, at each study visit, and at the end of treatment visit per the Schedule of Assessments (Table 1):

- Vitamin A deficiency: night blindness, blindness, dry eyes, hair loss
- Vitamin D deficiency: osteopenia, fractures, muscle weakness, impaired wound healing
- Vitamin E deficiency: muscle weakness, difficulty walking, tremors, vision problems, poor immune function
- Vitamin K deficiency: bleeding difficulties

If, despite vitamin supplementation, levels of one or more of the fat-soluble vitamins remain low and in the Investigator's opinion presents a significant risk to the patient, treatment with study drug should be interrupted. If the fat-soluble vitamin levels improve and are no longer considered to pose a serious risk, study drug may be restarted at the Investigator's discretion. Fat-soluble vitamin levels should be monitored.

### **10.2.3 Demographics/Medical and Surgical History**

Demographic information (age, full date of birth, gender, race, and ethnicity), along with medical and surgical history, will be obtained at Screening Visit 1, per country regulations.

Medical and surgical history will be obtained at Screening Visit 1. This includes date of diagnosis of ALGS, prior investigational medications for ALGS, historical (2 years prior to Screening) LFT values (AST, ALT, and total bilirubin), ongoing medication, any surgery performed, any other diagnosis, and historical biopsy data.

If a liver biopsy has been performed within 1 year prior to Screening, or during the study, the results will be recorded in the eCRF.

Medical History will be recorded at screening visits and randomization before the first dose of study drug.

### **10.2.4 Clinical Genetic Testing**

At Screening Visit 1, clinical genetic analysis to confirm mutations in either the JAG1 or NOTCH2 genes will be performed if the results are not available in the medical record. No other diagnostic genetic testing will be offered.

### **10.2.5 Physical Examination including Skin Examination**

A physician or suitably trained qualified assistant will perform a complete physical examination at Screening Visit 1 and Study Day 1. A complete physical examination will include assessment of general appearance, eyes, ears, nose, throat, head/neck/thyroid, lymph nodes, cardiovascular, lungs/chest, abdomen, genitourinary (if clinically indicated), extremities, skin, musculoskeletal, neurologic, and other.

Skin examinations of skin lesions due to scratching will be conducted at Screening Visit 2, Week 4 to 24/EOT, and Safety Follow-up visits (see [Table 1](#)). Skin will be examined thoroughly, and excoriations/scratch marks recorded. In addition, a symptom-directed physical exam will occur, with any findings recorded as medical history or AEs, as appropriate.

#### **10.2.6 Liver Ultrasound and Elastography**

Ultrasound of the liver and spleen will be performed at randomization (Study Day 1) and at Week 24/EOT. Liver size, echogenicity, and presence of masses/nodules will be recorded. Elastography will be performed as per institution standard practice where available.

#### **10.2.7 Vital Signs**

Evaluation of vital signs will be performed at all clinic visits. This includes blood pressure (systolic and diastolic), pulse, respiratory rate, temperature, height (or length depending on age), and body weight (using a certified weight scale) at clinic visits.

#### **10.2.8 Overdose**

Odevixibat is minimally absorbed and has a very low systemic availability. Based on toxicology data, for study purposes any dose exceeding a total of >3 mg/kg body weight of odevixibat taken as a single dose or as a cumulative dose within 24 hours is defined as an overdose.

The no adverse effect dose level in the most sensitive species (defined as 20 mg/kg/day) in the rat 1-month toxicity study gives a human equivalent dose of approximately 194 mg/day in a 60 kg person. This dose is approximately 10-fold higher than the maximum possible dose predicted in human studies (20 mg).

Any overdose is to be immediately (not later than within 24 hours of knowledge of the overdose) reported by the investigator or delegate on the Special Situations report form. In the event of an odevixibat overdose, the patient is to be monitored closely.

#### **10.2.9 Pregnancy**

If a pregnancy is discovered in a female patient enrolled in the study before the end of dosing, study drug will be permanently discontinued and an EOT visit will be scheduled. If the pregnancy is discovered in a female patient enrolled in the study after the end of dosing, the patient will continue in the study per protocol. If a pregnancy occurs in a male patient's partner at any time during the study, the pregnancy is to also be reported and followed.

Pregnancy is not considered to be an AE. However, if the patient has been dosed with the study drug, the pregnancy must be reported on the Pregnancy Notification Form within 24 hours of site awareness. Date of exposure and details of the period of gestation at the time of exposure is to be provided.

The pregnancy is to be followed to determine maternal and infant outcomes, including spontaneous termination, details of birth, and presence of any birth defects, congenital

anomalies or newborn or maternal complication. The infant who was exposed in-utero will be followed for up to 2 years after delivery. Any pregnancy that occurs within 90 days of the last dose of study drug must also be reported to the Sponsor.

### **10.3 Individual Study Drug Interruption and/or Discontinuation**

Study drug administration will be discontinued for the following:

- CTCAE Grade 3 or higher deemed possibly or probably related to study drug by the site Investigator.
- CTCAE Grade 4 or higher regardless of attribution to study drug.

### **10.4 Trial Discontinuation**

Trial discontinuation will be considered when any of the following occur:

- Three patients develop the same Grade 3 CTCAE attributed to study drug  
OR
- Two patients develop any Grade 4 CTCAE attributed to study drug  
OR
- One patient develops a fatal adverse event (Grade 5 CTCAE)

Events that could potentially trigger trial discontinuation will undergo an expedited review by Albireo's internal Safety Review Committee, which will reach an agreement prior to dosing new patients.

## 11 STATISTICAL EVALUATION

All personnel involved with the analysis of the study will remain blinded to treatment assignment until database lock is completed and until major protocol violations have been identified.

All statistical analyses will be performed using SAS version 9.4 or higher.

### 11.1 Sample Size and Power

Forty-five (45) patients <18 years of age will be randomized at an experimental to control allocation of 2 to 1 in order to obtain approximately 36 completers, assuming an approximate drop-out rate of 20%. Subjects <18 years of age will be randomized according one age stratification factor, i.e. <10, and 10 to <18 years of age. This stratification factor is based on Kamath et al. (2020), showing an increase in the prevalence and severity of pruritus in children <10 years of age. At a 1-sided significance level of  $\alpha_{1\text{-sided}} = 0.025$ , assuming a pooled standard deviation (SD) of 1.0, and a difference between the treatment groups of 1.2 in change of pruritus, favoring response, the power of the study is 0.909, using the exact method (Proc Power, SAS v.9.4, Cary, NC). The key secondary endpoint is also powered for a standardized treatment effect (treatment effect/SD) of 1.2.

#### 11.1.1 Sample Size Re-Estimation

After a minimum of 18 patients have completed the Week 16 visit, the pooled SD of change from baseline to Week 16 (Weeks 13 to 16 assessments) will be calculated by an independent statistician. Samples size re-estimation is based on non-comparative blinded data for which no alpha adjustment is required. If the pooled SD was underestimated in this original sample size calculation, an adjustment will be made to maintain study power, assuming a 1.2 treatment effect. It is assumed that the Week 16 and Week 24 SDs will be equivalent; however, a multiplication factor (e.g., 1.2) on the calculated SD may be made based on current understanding of the instrument at the time of sample size re-estimation. If SD was overestimated, in this original sample size calculation, the sample size will not be decreased.

### 11.2 Statistical Methods

#### 11.2.1 Statistical Analysis Sets

##### Safety Analysis Set

The safety analysis set will consist of all patients who received at least 1 dose of study drug. Patients will be analyzed according to the treatment they actually received. The safety analysis set will be the primary analysis set for safety analyses.

##### Full Analysis Set

The full analysis set (FAS) will consist of all randomized patients who received at least 1 dose of study drug treatment. Patients will be analyzed in the treatment group they were randomized to even if they received incorrect study drug. The FAS, excluding patients 18 years of age or older at randomization for whom the ObsRO is not utilized, will be the

primary analysis set for primary and key efficacy analyses. The FAS with all age groups will be utilized for all other secondary analyses.

### **Per Protocol Analysis Set**

The per protocol (PP) analysis set is a subset of the FAS, and will consist of all randomized patients for whom no major protocol violation (i.e. no violation which may affect the study efficacy outcome) is documented. The PP analysis set will provide supportive data for the efficacy analyses.

Allocation of patients to the PP analysis set will be performed before un-blinding of the study.

## **11.2.2 Methods of Statistical Analyses**

### **11.2.2.1 General Principles**

The primary objective of this study is to demonstrate the efficacy of repeated daily doses of 120 µg/kg/day odevixibat in relieving pruritus in patients with ALGS.

### **11.2.2.2 Missing Data**

There will be no imputation in the primary analyses of endpoints in this study as methods robust to missing data such as the mixed-effect model for repeated measures (MMRM) will be used. Each week, at least 4 of 7 assessments need to be completed for each of the AM and PM assessments. If these minimum assessments are not available, the week is considered missing. Monthly values will only be calculated if at least 3 weeks can be calculated. Sensitivity analyses including multiple imputation for missing data will be employed to assess the robustness of efficacy results and will be specified in the Statistical Analysis Plan.

### **11.2.2.3 Blinded Analyses to Confirm Responder Definitions**

A blinded analysis of Albireo ObsRO and PRO eDiary data will be performed after 50% or more of the planned sample has completed the Week 24 Visit. The blinded analysis will be used to estimate a threshold of clinically meaningful change (i.e., responder definition) in Albireo ObsRO and PRO pruritus scores. The analysis will be performed by a group independent from both the study team and Albireo. Blinded data will be used for this analysis; data will be collapsed across treatment groups.

The analyses will include distribution- and anchor-based analyses to examine a responder definition for the Albireo PRO/ObsRO pruritus scores. Distribution-based analyses will include calculation of the SD and standard error of measurement for the baseline Albireo PRO and ObsRO scores. Anchor-based analyses will involve examining the degree of change on the Albireo PRO and ObsRO scores from baseline to Week 24 for patients who experience change in pruritus according to PGIC and symptom items.

#### **11.2.2.4 Demographic and Baseline Characteristics**

Descriptive summaries of demographics and other baseline characteristics (including medical and surgical history) will be presented by treatment group and overall using the FAS.

Prior and concomitant medication use during the study will be summarized by treatment group and overall using the safety analysis set.

#### **11.2.2.5 Patient Disposition**

The following will be summarized (by treatment group and overall where applicable):

- Patients enrolled (who signed the informed consent)
- Patients randomized
- Patients treated
- Patients completing treatment
- Patients completing the study
- Patients discontinuing treatment early (including reason for discontinuation of treatment)
- Patients withdrawing early from the study (including withdrawal reason)

Additionally, patients enrolled, included in the safety, in the FAS, and in the PP analysis set will be summarized by region.

#### **11.2.2.6 Evaluation of Primary Efficacy Variables**

The FAS will be used as the primary analysis population. The primary endpoint is based on the worst scratching item 1 in the ObsRO AM and ObsRO PM ([Appendix 2](#)). The monthly (28-day) average for Months 1 through 6 in pruritis will be calculated by taking the average AM and the average PM weekly scores, then averaging the AM and PM weekly scores, and finally calculating the monthly average by averaging the 4 weeks within the month. Baseline is calculated similarly for the 14 days preceding start of treatment by taking the average AM and the average PM weekly scores, then averaging the AM and PM weekly scores, and finally calculating the average by averaging the 2 weeks. Change from baseline is calculated as the monthly score minus the baseline score.

The primary analysis for the primary endpoint will be determined from a MMRM modelling change from baseline for each four-week average pruritis score, with baseline age, baseline pruritus, baseline conjugated bilirubin, treatment group, time (in months), and treatment-by-time interaction in the model. A MMRM will be used to compare treatment effects at Month 6.

Sensitivity analyses based on different missing data mechanisms, and for different population subgroups will be conducted as described in the Statistical Analysis Plan. The PP analysis set will also be used as a sensitivity analysis.

The primary objective of the study is to assess the efficacy of odevixibat in relieving pruritus in patients with ALGS. To avoid confounding of the treatment effect, the data collected following an intercurrent event will not be included in the primary analysis. Intercurrent events will be defined in the Statistical Analysis Plan.

Additional analyses including all data collected through the end of the study regardless of intercurrent events will also be performed.

#### **11.2.2.7 Evaluation of Additional Efficacy Variables**

There will be no alpha adjustment for multiple hypothesis testing as these additional efficacy variables are supportive, only. For efficacy variables in which change from baseline is assessed, MMRM will be used as the primary analysis methodology in the FAS population. Sensitivity analyses will be performed as defined in the Statistical Analysis Plan.

#### **11.2.2.8 Evaluation of Safety Variables**

Safety data will be analyzed using descriptive statistics and summaries by treatment group of SAEs, AEs, vital signs, clinical laboratory tests (hematology, clinical chemistry, and urinalysis), and concomitant medication. Analyses will be performed using the safety analysis set.

Summaries of AEs (coded according to the Medical Dictionary for Regulatory Activities [MedDRA] system organ class [SOC] and MedDRA preferred term) will include the following:

- Overview of the incidence of TEAEs (TEAEs, drug related TEAEs, TEAEs leading to study discontinuation, and treatment emergent SAEs)
- TEAEs by SOC and preferred term
- Intensity of TEAEs by SOC and preferred term
- Drug related TEAEs by SOC and preferred term
- TEAEs leading to study discontinuation by SOC and preferred term
- Treatment emergent SAEs by SOC and preferred term

Concomitant medication use during the treatment period will be summarized by Anatomical Therapeutic Chemical class and World Health Organization preferred name.

Summaries of vital signs will be presented. For each visit, the actual results and the change from baseline, and the number and percentage of patients with potentially clinically significant (PCS) values observed post-baseline will be presented.

Summaries of clinical safety laboratory data will be presented. For each visit, the actual result and the change from baseline, and the number and percentage of patients with PCS values observed post-baseline will be presented.

Data listings will be provided for each patient for all safety parameters.

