### 7.2.2 Exclusion Criteria

1. Patient with past medical history or ongoing presence of other types of liver disease including, but not limited to, the following:
  - a) Biliary atresia of any kind
  - b) PFIC
  - c) Benign recurrent intrahepatic cholestasis
  - d) Suspected or proven liver cancer or metastasis to the liver on imaging studies

2. Patient with a past medical history or ongoing presence of any other disease or condition known to interfere with the absorption, distribution, metabolism (specifically bile acid metabolism), or excretion of drugs in the intestine, including but not limited to, inflammatory bowel disease
3. Patient with past medical history or ongoing chronic (i.e. >3 months) diarrhea requiring intravenous fluid or nutritional intervention for treatment of the diarrhea and/or its sequelae
4. Patient has a confirmed past diagnosis of infection with human immunodeficiency virus or other present and active, clinically significant chronic infection
5. Recent infection requiring hospitalization or treatment with parenteral anti-infective within 4 weeks of randomization (Study Day 1) or completion of oral anti-infective treatment within 2 weeks prior to start of Screening Period
6. Cancer within the last 5 years except for basal cell carcinoma
7. Cancer >5 years prior to screening except for non-liver cancers with no evidence of recurrence
8. Chronic kidney disease with an impaired renal function and a glomerular filtration rate <70 mL/min/1.73 m^2
9. Patient with surgical history of disruption of the enterohepatic circulation (biliary diversion surgery) within 6 months prior to start of Screening Period
10. Patient has had a liver transplant or a liver transplant is planned within 6 months of randomization
11. Decompensated liver disease, history or presence of clinically significant ascites, variceal hemorrhage, and/or encephalopathy
12. INR >1.4 (the patient may be treated with Vitamin K intravenously, and if INR is ≤1.4 at resampling the patient may be randomized)
13. Serum ALT >10 × ULN at Screening
14. Serum ALT >15 × ULN at any time point during the last 6 months unless an alternate etiology was confirmed for the elevation
15. Total bilirubin >15 × ULN at Screening
16. Patient suffers from uncontrolled, recalcitrant pruritic condition other than ALGS. Examples include, but not limited to, refractory atopic dermatitis or other primary pruritic skin diseases

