4.8.2 Additional Safety Assessments

4.8.2.1 Laboratory Variables

The following laboratory variables will be analyzed.

- Hematology:
 - Red blood cells and platelets: hemoglobin, hematocrit, red blood cell count, and platelet count
 - White blood cells: white blood cell count, neutrophils, lymphocytes, monocytes, basophils, and eosinophils
- Clinical chemistry:
 - Metabolism: total cholesterol, triglycerides, creatine kinase, albumin
 - Electrolytes: sodium, potassium, chloride, calcium
 - Renal function: creatinine, blood urea nitrogen, estimated glomerular filtration rate
 - Liver function: ALT, AST, Alkaline phosphatase (and isoenzymes as applicable), direct bilirubin, total bilirubin, gamma-glutamyl transferase
 - Pregnancy test: Serum β -human chorionic gonadotropin (all female patients with positive urine pregnancy test)
- Urinalysis:
 - Urinalysis for quantitative analysis: pH, proteins, glucose, blood, ketones, leukocytes, and nitrites
- Other Labs: Vitamin A and E, 25-hydroxy vitamin D, INR, Alfa-fetoprotein (AFP), and Prothrombin Time

Quantitative analyses

For all laboratory variables above, descriptive statistics for clinical laboratory values (in SI units for all tests, and in conventional units for selected tests (Appendix 8) and absolute changes from baseline at each post-baseline visit (Appendix 3) will be presented. The change to the last visit will also be summarized. Central laboratory data will be used for the summary. If central laboratory data are not available due to COVID-19 or other reasons, local laboratory data will be used if available.

Figure for ALT, AST, total bilirubin, ALP, and gamma-glutamyl transferase will be presented as individual patient trellis plot over time.

Analyses according to reference normal range

Shift tables from baseline to the highest and lowest post-baseline value for quantitative variables will be presented for the clinical laboratory parameters. The laboratory results will be classified as low, normal, and high based on the normal range that provided by central/local laboratories.

For ALT, AST and total bilirubin, a shift table based on the following classifications (per DILI guidance and CTCAE) will be presented:

[figure not shown]
- ALT and AST: ≤ 3 ULN, > 3 and ≤ 5 ULN, > 5 and ≤ 10 ULN, > 10 ULN
- Total Bilirubin: ≤ 2 ULN and > 2 ULN

Liver monitoring

A listing of patients meeting the criteria for liver monitoring (Table 7) will be provided.

Table 7 – Liver monitoring

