4.8.2.2 Vital Signs

Descriptive statistics for vital signs [blood pressure (systolic and diastolic), pulse, respiratory rate, temperature, height (or length depending on age), body weight (using a certified weight scale), and BMI] and their changes from baseline at each post-baseline visit will be presented. The change to last visit will also be summarized. Shift tables for the number of patients with changes from baseline to highest and lowest post-baseline value based on the normal ranges as outline in [Appendix 7](#) will be provided.

If height is collected as length, it will be converted as following:

$$\text{Height (cm)} = \text{length (cm)} - 0.7 \text{ cm.}$$

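### The SAP omits the protocol's counts of patients with potentially clinically significant laboratory and vital-sign values, and most of its laboratory shift tables cannot show further worsening in patients already abnormal at entry

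*Protocol*

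**What the plan says.** Protocol 11.2.2.8 (Evaluation of Safety Variables) sets out three by-visit summaries for vital signs: the result, its change from baseline, and a count, so that "the number and percentage of patients with potentially clinically significant (PCS) values observed post-baseline will be presented". The following paragraph repeats this for safety laboratory data: "the number and percentage of patients with PCS values observed post-baseline will be presented". PCS is in the protocol's abbreviation list, but neither document gives a PCS cut-off.

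SAP 4.8.2.1 keeps descriptive statistics for laboratory values and "absolute changes from baseline at each post-baseline visit". Its general categorical summary is: "Shift tables from baseline to the highest and lowest post-baseline value for quantitative variables will be presented for the clinical laboratory parameters". The categories are: "The laboratory results will be classified as low, normal, and high based on the normal range that provided by central/local laboratories".

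There is one exception: "For ALT, AST and total bilirubin, a shift table based on the following classifications (per DILI guidance and CTCAE) will be presented". ALT and AST have four levels (up to 3, above 3 to 5, above 5 to 10, and above 10 × ULN). Total bilirubin has two, divided at 2 × ULN. The section also plans individual-patient trellis plots for ALT, AST, total bilirubin, ALP and GGT, and a listing of patients who meet the liver-monitoring criteria.

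For vital signs, SAP 4.8.2.2 plans by-visit descriptive statistics and "Shift tables for the number of patients with changes from baseline to highest and lowest post-baseline value based on the normal ranges" in Appendix 7.

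PCS does not appear in the SAP's abbreviations, safety sections or derivations. Neither the version history (SAP Table 1) nor Appendix 1 (SAP Table 8) mentions its removal.

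**The concern.** A between-arm count promised in the protocol has disappeared without a record. What replaces it suits this population poorly. Protocol 5.2 says that about 95% of patients with ALGS present with chronic cholestasis, with raised liver tests and conjugated hyperbilirubinaemia. The entry criteria require bile acids above ULN and accept INR up to 1.4, ALT up to 10 × ULN and total bilirubin up to 15 × ULN. Many patients will therefore already be out of range on the tests where liver harm or vitamin malabsorption would show.

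A three-category shift registers a patient crossing a limit of normal. It does not register a patient beyond that limit moving further away. With about 30 and 15 patients per arm, one or two marked excursions are what a safety reader looks for, and a count by arm is the direct way to show them.

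**Working it through.** The plan states no figure on this point, so there is none to reproduce. The check is a comparison of text, then a test of what each planned table can register.

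**1. Promise against plan**

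| Item | Protocol 11.2.2.8 | SAP 4.8.2.1 and 4.8.2.2 |
|---|---|---|
| Result and change by visit | yes | yes |
| Count and % with PCS values by visit, laboratory | yes | absent |
| Count and % with PCS values by visit, vital signs | yes | absent |
| Removal recorded | – | no; Appendix 1 lists four other changes (PP set, direct bilirubin, least-squares means, growth) |

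**2. What the shift tables register**

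The values below are assumed, in multiples of ULN, and are run through the SAP's own cut-points.

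| Test, baseline to worst | Low/normal/high table | Graded table |
|---|---|---|
| ALT 4 to 9 | high to high | >3–≤5 to >5–≤10 (visible) |
| ALT 6 to 14 | high to high | >5–≤10 to >10 (visible) |
| ALT 5.5 to 9.9 | high to high | no shift |
| Total bilirubin 1.5 to 6 | high to high | ≤2 to >2 (visible) |
| Total bilirubin 3 to 12 | high to high | no shift |
| Total bilirubin 10 to 20 | high to high | no shift |

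The ALT and AST grading recovers much of the worsening. The single bilirubin cut recovers none of it in a patient who enters above 2 × ULN. GGT, ALP, direct bilirubin, INR, cholesterol and the vitamins have no graded table. For example, an INR going from 1.3 to 2.0 (actual values, assuming a laboratory upper limit below 1.3) is high to high and appears in no other shift table.

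**3. How many patients one such table can inform on**

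- Arms: 45 randomised 2:1 gives 45 × 2/3 = 30 and 45 × 1/3 = 15.
- Let p be the share already above ULN at baseline for a given test. The documents do not give p; assume 0.8 to 1.0.
- Patients able to show an upward shift = (1 − p) × arm size.
- p = 0.8: 0.2 × 30 = 6 and 0.2 × 15 = 3.
- p = 1.0: 0 and 0.

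The other 24 to 30 odevixibat and 12 to 15 placebo patients cannot shift upward in that table, whatever happens on treatment.

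**4. Where else a marked value could appear**

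- Minimum and maximum are part of the SAP 4.1 descriptive statistics and are given by arm and visit. SAP Appendix 3 keeps the value nearest the target day in each window, so an off-target excursion can be left out.
- Trellis plots cover five liver tests. INR, direct bilirubin, cholesterol and the vitamins have none.
- The liver-monitoring output is a listing limited to the SAP Table 7 criteria.
- The INR >1.5 rule in SAP Table 6 applies only to reported adverse events with the refractory-to-vitamin box checked. It is not a laboratory count.

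None of these gives a number and percentage by arm of patients with marked laboratory values.

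**The case against.** The strongest reply is that marked values will not go unseen. Maxima and minima are tabulated by arm and visit. Every patient's course is plotted for five liver tests, including GGT and ALP. ALT and AST have four-level shifts. SAP 4.6.4.1 models ALT, AST, GGT, direct and total bilirubin and cholesterol with graphs. Deterioration that the investigator judges clinically significant becomes an adverse event (Protocol 10.1.2.2) and is tabulated by CTCAE grade. Fat-soluble vitamin deficiency refractory to supplementation is counted by arm and has a supporting listing merged with laboratory data. Safety is descriptive throughout, and the table shells are in a separate document.

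Most of this stands, and it rules out several stronger readings.

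- A reader might infer that only means and medians remain, so that a single large excursion would vanish. The documents do not support that: minimum, maximum and individual plots are planned.
- A reader might infer that the protocol's analysis would have caught worsening in patients abnormal at entry. PCS is never defined, and a fixed cut-off can have the same ceiling, so this cannot be asserted.
- A reader might extend the already-abnormal argument to vital signs. Nothing in the documents suggests abnormal vital signs at entry, and the normal-to-low and normal-to-high cells already show new abnormalities. The gap there is the by-visit count and the missing record.

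What the reply does not supply is the promised count. The adverse event routes depend on reporting and judgement. Shells that contained PCS tables would still have no criteria to apply.

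**Conclusion.** The point holds and should be corrected. The PCS counts are missing from the SAP for both laboratory values and vital signs, and the omission is unrecorded. For laboratory tests other than ALT, AST and total bilirubin, the only categorical summary cannot show further worsening in patients already out of range. For total bilirubin the single cut at 2 × ULN leaves the same gap from 2 × ULN up to and beyond the 15 × ULN entry limit.

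The figure of at most 6 of 30 and 3 of 15 patients able to shift upward rests on the assumed 80% to 100% abnormal at baseline. It describes one table, not the whole safety output. The conclusion also assumes that the separate table shells hold no PCS criteria. The consequence is a weaker between-arm safety display in a small paediatric liver-disease trial. Efficacy inference is untouched.

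**What to change.** Before unblinding:

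- **Laboratory (SAP 4.8.2.1).** Restore the number and percentage by arm, at each visit and at the worst post-baseline value. Count all treated patients and show the baseline category. Restricting the count to patients not beyond the cut-off at baseline would again leave out the most affected.
- **Categories.** Use the CTCAE v5.0 grading that the protocol already applies, where it grades the test, and INR >1.5 from SAP Table 6 as an analysis category. For tests abnormal at entry, add a baseline-relative criterion in multiples of the patient's own baseline value. Fix all cut-offs in one table.
- **Total bilirubin.** Add finer categories above 2 × ULN.
- **Vital signs (SAP 4.8.2.2).** Add by-visit counts outside the Appendix 7 ranges, or record and justify the omission in Appendix 1.

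The cost is SAP wording, one cut-off table and a few descriptive tables from data already collected. The small downside is more safety output to read.
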